4.3 Endpoints

4.3.1 Primary endpoint

Incidence of Ng plus Ct detected at any site whilst individuals are screened vs. not screened.

Numerators: Cumulative number of diagnoses of Ng plus Ct in 12 months in screening/non-screening arms. Each participant can only contribute one diagnosis of Ct and one diagnosis of Ng per (scheduled or unscheduled) visit - regardless of number of sites infected. Thus each participant can contribute up to 2 diagnoses (Ct/Ng) at each (scheduled or unscheduled) visit. The numerator includes laboratory-confirmed diagnoses made between scheduled visits, performed inside or outside of the study.

Denominators: Number of scheduled study visits with available results for the diagnosis of Ng/Ct. The denominator does not include unscheduled visits^a.

The diagnosis of Ng and Ct will be made via nucleic acid amplification testing (NAAT) performed on rectal and pharyngeal swabs and urine.

In the primary analysis, the primary endpoint (as described above) includes all Ng/Ct diagnoses. Hence it is implicitly assumed that every diagnosis is a new infection. It is however possible that an Ng/Ct infection detected at the 3 to 12 month visit in the non-screening arm is simply a non-resolved infection from the prior visit (see Figure 5)^b. This could spuriously increase the measured incidence in the non-screening group. Because

^a The rationale for this definition of the denominator is to, as closely as possible, reflect time at risk of testing Ng/Ct positive. If an individual misses one of their 4 study follow up visits then this reduces their probability of being diagnosed with Ng or Ct by one quarter (assuming no other relevant variables change). Our denominator definition takes this into account by only including study visits where we have results of Ng/Ct testing. Unscheduled visits are not included as these make up a very small proportion of all visits and could be considered to bias the time at risk estimate.

[figure not shown]
^b Given the natural rate of clearance of Ng and Ct from each site, this probability is very low

this risk only applies to the non-screening arm it results in a bias towards exaggerating the effect of screening on incidence. As such if our study finds that non-screening is non-inferior to screening this finding could not be explained by this bias. In a sensitivity analysis, the numerator of the primary endpoint will only include diagnoses if there was a negative test result at the prior visit.

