5 TRIAL DESIGN

This study is a multi-centre, controlled, randomized trial of 3x3 Ng/Ct screening (comparator) vs. no screening (intervention). It will be performed in the PrEP cohorts situated at the ITM, HSP, CHU, UZG and EH. All men in follow up at these five centres who report having had sex with another man in the previous year and are enrolled for PrEP follow up will be eligible to participate in the study. After signing informed consent participants will be randomized via a computer-generated schema to either 3x3 screening or no Ng/Ct screening (see section 8.3). In both arms, participants will be followed up in an identical fashion including 3x3 screening. The only difference between the arms will be that in the screening arm, Ng/Ct results will be sent by the STI Laboratory to the study physicians and these participants will be treated and partner contact tracing will be done. The STI Laboratory will only process the samples/report the results from the non-screening arm at the end of the study. In both arms, all individuals with symptoms compatible with Ng or Ct will be tested and treated for these infections according to current best practice guidelines. At the end of the 12-month study period, participants whose most recent tests were positive for Ng or Ct will receive treatment for these.

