- **Day-of-visit testing.** The tests for Ng/Ct and other laboratory tests are performed on the day of the clinic visit. The participant is typically contacted the following week in the event of an abnormal laboratory test for further treatment/intervention.
- **Week-prior testing.** Here the laboratory tests are performed the week prior to the clinic visit and the results are available to discuss during the clinic visit.

The results of these tests will be used for documentation purposes after the participant has given consent to participate. The test itself is to be considered as a standard of care screening test.

In the event of a positive test for Ng/Ct at this screening visit, they will receive appropriate therapy regardless of which arm they are assigned to.

If an individual has ***symptomatic*** urethritis or proctitis at the time of the study visit they will not be eligible for study enrolment at that visit. They will however be eligible for enrolment at one of their subsequent study visits if their symptoms have resolved by this time point.

Testing positive for syphilis and receiving treatment for syphilis is not an exclusion criteria for participation at the screening or any other visit.

Eligibility for study participation will be confirmed by the study doctors. Study participants will not receive any reimbursement for participation.

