8.7 Trial assessments

These assessments will be performed according to standard of care at each participating centre. In certain centres such as HSP the laboratory tests are performed the week before the clinic visit. These laboratory assessments will be considered to be the laboratory results for that particular visit. Participants in the non-screening arm will not be informed of their results at month 3, 6 and 9. They will only be informed about the result of the sample taken at month 0 and month 12.

Screening/enrolment visit (Day 0):

- Eligibility check
- Informed Consent Procedure
- Demographic and question regarding sexual behaviour
- PrEP questionnaire (only at ITM)
- Ask if symptoms compatible with STI
- Physical examination if symptomatic
- STI history last 12 months
- Antibiotic usage last 6 months
- Randomization
- Collection of results of syphilis and HIV testing (performed according to routine practice)
- Sample collection (according to standard practice of the participating sites.):
 - o Urine sample (first-void) (Ng/Ct NAAT)
 - o Pharyngeal swab (Ng/Ct NAAT)
 - o Anorectal swab (Ng/Ct NAAT)

Visit month 3 (can be between one week earlier and 6 weeks later):

- Ask if symptoms compatible with STI
- Physical examination if symptomatic
- STIs diagnosed since last visit (at study site or outside)
- Antibiotic usage
- Question regarding sexual behaviour
- PrEP questionnaire (only at ITM)
- Collection of results of syphilis and HIV testing (performed according to routine practice)

- Sample collection:
 - o Urine sample (first-void) (Ng/Ct NAAT)
 - o Pharyngeal swab (Ng/Ct NAAT)
 - o Anorectal swab (Ng/Ct NAAT)

Visit month 6 (can be between one week early and 6 weeks late):

- Ask if symptoms compatible with STI
- Physical examination if symptomatic
- STIs diagnosed since last visit (at study site or outside)
- Antibiotic usage
- Question regarding sexual behaviour
- PrEP questionnaire (only at ITM)
- Collection of results of syphilis and HIV testing (performed according to routine practice)
- Sample collection:
 - o Urine sample (first-void) (Ng/Ct NAAT)
 - o Pharyngeal swab (Ng/Ct NAAT)
 - o Anorectal swab (Ng/Ct NAAT)

Visit month 9 (can be between one week early and 6 weeks late):

- Ask if symptoms compatible with STI
- Physical examination if symptomatic
- STIs diagnosed since last visit (at study site or outside)
- Antibiotic usage
- Question regarding sexual behaviour
- PrEP questionnaire (only at ITM)

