11.1 Sample size calculation

The primary endpoint is the number of diagnoses of Ng plus Ct over the study period (12 months) whilst individuals are screened vs. not screened.

Numerators: Cumulative number of diagnoses of Ng plus Ct in 12 months in screening/non-screening arms. Each participant can only contribute one diagnosis of Ct and one diagnosis of Ng per (scheduled or unscheduled) visit - regardless of number of sites infected. Thus each participant can contribute up to 2 diagnoses (Ct/Ng) at each (scheduled or unscheduled) visit. The numerator includes laboratory-confirmed diagnoses made between scheduled visits, performed inside or outside of the study.

Denominators: Number of scheduled study visits with available results for the diagnosis of Ng/Ct. The denominator does not include unscheduled visits.

Testing for these infections is performed at each three-monthly visit, i.e. 4 follow-up visits per subject (if complete follow up). Ng/Ct are tested for at 3 sites at each visit – rectum/pharynx and urethra. If a participant is found to be infected with one of these infections at more than one site on a particular visit this is counted as a single infection. If they are found to have both Ng and Ct at a visit this is classified as 2 infections.

Based on the Be-PrEP-ared study from ITM, we assume at baseline visit 79% have 0 diagnoses (pre treatment), 18% have 1 diagnosis (either NG or CT) and 3% has 2 diagnoses (both NG and CT). With screening, the number of diagnoses in the Follow Up (FU) visits depends on number of diagnosis at baseline and is shown below.

	0 diagnoses [#]	1 diagnosis [#]	2 diagnoses [#]	Average nr of diagnoses
0 diagnoses at baseline	86%	13%	1%	0.15
1 diagnosis at baseline	76%	20%	4%	0.28
2 diagnoses at baseline	71%	24%	5%	0.34

[#]These columns refer to the percentage of participants who have 0/1/2 diagnoses at each follow-up visit. In other words, of those with 0 diagnoses at baseline (first row), at each of the visits at 3,6,9 and 12 months, 86% will have 0 diagnoses, 13% will have 1 diagnosis and 1% will have 2 diagnoses.

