Over 4 FU visits, this yields an average of 0.72 diagnoses per subject. Using a Poisson regression model with $\log(\text{number of visits})$ as offset, the 95% confidence interval of the log ratio (no screening vs. screening) is calculated. The 'no screening' arm is considered to be non-inferior if there is an increase of maximal 25% in number of diagnoses (i.e. increase of an average of 0.72 to 0.90 per 4 visits). The 'no screening' arm is proven to be non-inferior if the upper limit of the 95% confidence interval is lower than $\log(1.25)$. The required sample size to detect non-inferiority of the 'no screening' arm is calculated by simulation, assuming no difference between arms.

Assuming that 95% of the participants will have data on all 4 visits, and 5% will have data on only 3 visits, the required sample size to obtain 80% power is 912. Assuming an additional 10% drop out rate we will need to enroll 1014 participants.

The current number of PrEP participants at the ITM/HSP/EH/CHU/UZG is 803/739/290/260/240, respectively. At all 5 centres this number is increasing by approximately 20% per year. 99.7% of these individuals are MSM and over the age of 18. We estimate that 80% of the 2332 PrEP participants in these five centres will agree to participate. This number (n=1866) exceeds the number we need to enroll in the study (n=1014). By the commencement of the study (begin 2020) we estimate we will have 1518/886/464/314/298 individuals in the PrEP cohorts at the ITM/HSP/EH/CHU/UZG whom we will be able to screen for participation.

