Interim analyses are planned at two time points: once 50% and 100% of all study recruits have passed their 6 month visit. For the first interim analysis, data is used of the first 507 enrolled participants (i.e. ordered by randomization date) until 6 months follow-up. For the second analysis, data is used of all enrolled participants until 6 months follow-up. The goal of the interim analyses (at both time points) is to estimate the incidence rate ratio of symptomatic Ng plus CT. Estimates will be based on a Poisson regression model (or a negative binomial regression model if there is overdispersion) with number of symptomatic diagnoses as dependent variable, arm and hospital as independent variables and log(number of visits) as offset. This model will provide estimates of the incidence rate in each arm and the incidence rate ratio (no screening versus screening), together with 95% confidence interval. Visits with missing data on the diagnosis of Ng or Ct, will be excluded from the calculation of the incidence rate (excluded both from numerator and denominator).

7. Analysis of main efficacy outcomes: Incidence of Ng plus Ct

In each arm, the incidence of Ng plus Ct will be estimated together with 95% confidence interval. Estimates will be based on a Poisson regression model (or a negative binomial regression model if there is overdispersion) with number of diagnoses as dependent variable, arm and hospital as independent variables, and log(number of visits) as offset. This model will also provide an estimate of the log incidence rate ratio (no screening versus screening), together with 95% confidence interval. The 'no screening' arm is proven to be non-inferior if the upper limit of the 95% confidence interval is lower than $\log(1.25)$.

Visits with missing data on the diagnosis of Ng or Ct, will be excluded from the calculation of the incidence rate (excluded both from numerator and denominator).

In a sensitivity analysis, the numerator of the primary endpoint will only include diagnoses if there was a negative test result at the prior visit.

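### Planned care is the same in both arms until the month-3 sample, so the four-visit margin of 1.25 corresponds to about 1.33 over months 6-12, and neither document says so

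*Protocol*

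**What the plan says.** - **Month 0.** Protocol 8.1.2 treats anyone positive at the screening visit in either arm: "they will receive appropriate therapy regardless of which arm they are assigned to".
- **Results withheld.** Protocol 8.7: "Participants in the non-screening arm will not be informed of their results at month 3, 6 and 9". It continues: "They will only be informed about the result of the sample taken at month 0 and month 12".
- **Contrast between arms.** Protocol 5, repeated in SAP 2.1: "The only difference between the arms will be that in the screening arm, Ng/Ct results will be sent by the STI Laboratory" to the physicians, with treatment and contact tracing following from that. Symptomatic participants are tested and treated in both arms.
- **Endpoint.** In Protocol 4.3.1 and SAP 5.2 the numerator is all laboratory-confirmed diagnoses over 12 months, including those made between visits. The denominator is "Number of scheduled study visits with available results for the diagnosis of Ng/Ct". Complete follow-up means four visits (months 3, 6, 9 and 12), and month 3 is not set apart.
- **Margin.** Protocol 11.1 accepts the no-screening arm as non-inferior if "there is an increase of maximal 25% in number of diagnoses", worked through as 0.72 rising to 0.90 per four visits. SAP 7 tests the upper 95% limit against log(1.25).
- **Bias discussed.** Both documents consider only non-resolved infection in the no-screening arm, which inflates that arm's rate. The sensitivity analysis they plan for it counts a diagnosis only after a negative test at the prior visit, and it keeps month 3.

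**The concern.** A month-3 positive reflects infection acquired, or left uncleared, between month 0 and month 3. Over that interval both arms have been tested, informed and treated under the same plan. Withholding a result can first change what happens after the month-3 sample. A quarter of the scheduled visits therefore carries no information about the planned contrast. If stopping screening does raise incidence, including those visits moves the ratio towards 1, which is the favourable direction in a non-inferiority trial.

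A positive result is meant to support a recommendation to stop screening (Protocol 2 and 11.4). A reader will naturally take 25% as the increase tolerated when screening stops, whereas the design tolerates more than that over the visits where stopping can act. The documents say that a non-inferiority finding could not be explained by the bias they discuss. They mention no influence running the other way, and they plan no analysis confined to the period in which care differs.

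**Working it through.** **Inputs (Protocol 11.1).** Baseline mix is 79/18/3% with 0/1/2 diagnoses. Mean diagnoses per follow-up visit are 0.15, 0.28 and 0.34 in those groups. 95% of participants have four visits and 5% have three. Evaluable N is 912, allocated 1:1, with margin 1.25 and a two-sided 95% interval.

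**Reproducing the plan's figure.**
- Mean per visit: 0.79×0.15 + 0.18×0.28 + 0.03×0.34 = 0.1791. Over four visits this is 0.716, matching the stated 0.72.
- Average visits: 0.95×4 + 0.05×3 = 3.95. Events per arm: 456×0.1791×3.95 = 322.6.
- Power at ratio 1: SE = √(2/322.6) = 0.0787, and Φ(0.2231/0.0787 − 1.96) = 80.9%. Simulation from the protocol's table, with a Poisson model and site omitted, gives 80.4%. The stated 80% at 912 is reproduced, and 912/0.9 = 1014.

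**Translating the margin.** Take equal rates at month 3 and a constant ratio R at months 6, 9 and 12. The four-visit ratio is (1 + 3R)/4.
- Setting this to 1.25 gives R = (4×1.25 − 1)/3 = 1.33.
- In the protocol's own counts: of 0.72 and 0.90 diagnoses, month 3 supplies 0.18 in each arm, leaving 0.54 and 0.72. The ratio 0.72/0.54 is 1.33.

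**Chance of declaring non-inferiority at R = 1.25.**
- Pooled ratio: (1 + 3.75)/4 = 1.1875.
- Events: 322.6 and 322.6×1.1875 = 383. SE = √(1/322.6 + 1/383) = 0.0756.
- Φ((log 1.25 − log 1.1875)/0.0756 − 1.96) = Φ(−1.28) = 10.0%. Simulation gives 10.2%.

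Simulated chance of an upper limit below log(1.25), N = 912:

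| R over months 6-12 | Four-visit ratio | Four visits | Months 6-12 only |
|---|---|---|---|
| 1.00 | 1.00 | 80% | 68% |
| 1.10 | 1.075 | 50% | 31% |
| 1.20 | 1.15 | 20% | 7% |
| 1.25 | 1.1875 | 10% | 2.3% |
| 1.33 | 1.25 | 3.2% (closed form 2.5%) | 0.5% |

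**Cost of dropping month 3.** Events per arm fall to 0.75×322.6 = 241.9, SE rises to 0.0909, and closed-form power at ratio 1 is 68.9% (68.5% simulated). Model variants run from about 66% with robust errors to about 69% with baseline adjustment. With no true difference, about 13-14% of trials pass the four-visit test but do not reach 1.25 on months 6-12.

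**The case against.** **The margin is defined on four visits.** The primary objective is incidence over 12 months, and Protocol 11.1 sets 25% on the four-visit total. Stopping routine screening after a tested and treated baseline is the strategy under study, so counting its first three months is a defensible estimand. This stands. A reader might infer that the trial's false-positive rate is 10% instead of 2.5%. The documents do not support that: at R = 1.25 the four-visit ratio is 1.19, inside the stated margin, and the test keeps its nominal error against the hypothesis the protocol wrote. Nor do they support removing month 3 from the primary analysis. At R = 1 it dilutes nothing and adds precision.

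**Months 6-12 concentrate the opposite bias.** Carry-over needs an untreated positive at the previous visit. Month-0 positives are treated, so carry-over falls almost wholly in months 6-12 of the no-screening arm. Protocol 1 has asymptomatic infection persisting for one to 6 months, although Protocol 4.3.1 calls carry-over very unlikely. Suppose, as an assumption, that 10% or 20% of untreated positives still test positive three months later, with no true effect. The months 6-12 ratio is then 1.08 or 1.17 (four-visit 1.06 or 1.13), and non-inferiority is reached in 38% or 13% of trials on months 6-12, against 56% or 30% on four visits. This also stands. A months 6-12 ratio cannot be read as a pure screening effect, and the net of the two biases cannot be computed from the documents.

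**Equal care before month 3 is the plan, not a certainty.** Doctors are unblinded and behaviour could diverge. Protocol 8.4 says no-screening participants who log in within three weeks of enrolment see no result, which conflicts with disclosure of the month-0 result in 8.7; the two sections need reconciling. Treatment of month-0 positives in both arms under 8.1.2 is unaffected. Equal month-3 rates therefore remain an assumption to be stated.

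**Applying 1.25 to months 6-12 alone is stricter than the plan's margin.** Correct, which is why that analysis should not gate the conclusion.

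**Conclusion.** The concern holds as a gap in interpretation and in the planned analyses. If stopping screening has an effect, the four-visit ratio understates it over the period when planned care differs, and 1.25 corresponds to about 1.33 there. A true 25% increase over months 6-12 would be declared non-inferior in about 10% of trials, against 2-3% on those visits alone.

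The figures assume equal month-3 rates, constant R over months 6-12, missed visits at random, and no carry-over. The one-quarter share is exact for scheduled visits. For diagnoses it holds when rates are equal; at R = 1.33 month 3 supplies 1/(1+4) = 20% of the no-screening arm's diagnoses.

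The primary test is not invalid. What is missing is a statement of what its margin means once care differs, and an analysis that shows it.

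**What to change.** Keep the four-visit primary analysis and its margin. Add to SAP 7, before unblinding:

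1. A supportive, non-gating analysis of scheduled visits at months 6, 9 and 12 and of between-visit diagnoses after month 3. It uses the primary model, adjusted for the month-0 result.
2. Its rate ratio and 95% interval reported beside the primary, read against both 1.25 and the translated value of about 1.33.
3. A repeat with the already planned restriction to diagnoses with a negative prior test, because carry-over sits almost wholly in these visits.
4. A sentence in the report that the four-visit margin corresponds to about 1.33 over months 6-12 if month-3 rates are equal between arms.

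The cost is SAP wording and one extra analysis, with its repeat, on data already collected. Sample size, endpoint and participant care do not change. The downside is power of about 66-70% against 1.25 at no true difference. Discordance is also possible by chance alone: about 13-14% of trials with no true difference would pass the primary but not reach 1.25 here. The SAP should say in advance that such a result qualifies the primary conclusion and does not overturn it.

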8.2 Consent

The Informed Consent Form (ICF) documents will be designed in accordance with the requirements of the Helsinki Declaration (2013), the E6 ICH GCP Guidelines (2016) and the Belgian Law on Experiment on the Human Person (2004). The ICFs will be developed in Dutch, French and English. Translation(s) will be done using DeepL translation software (www.deeple.com). Translations will subsequently be reviewed and validated and a translation validation form will be completed and signed by the reviewer. The IC procedure will describe the purpose of the study, the procedures to be followed, the risks and benefits of participation, confidentiality issues, etc. The ICF will include an option for the participant to consent with long-term storage of the samples for future research.

All informed consent procedures will be conducted by qualified staff members identified by the principal investigator and done in the language chosen by the participant. Participants will be informed that participation in the study is completely voluntary and that they may withdraw from the study at any time without giving reasons and without any negative consequences. Participant Information Sheets (PIS) and consent forms will be provided to the study participants for review. The participants will be given enough time to consider whether or not to participate in the study. Upon agreement on participation, the consent form will be signed in two copies, namely by the participant and by the study investigator or designee administering the consent. The participant will receive one copy of the ICF, while the other copy will remain in the Investigator file. If a participant is unable to read or write, a signature from a witness to the informed consent discussion will be obtained.

No participant may be enrolled in the study (and no study-specific procedures will be performed) until the study investigator or designee has obtained his informed consent.

The ITM, or site-specific, Standard Operating Procedure (SOP) for 'Obtaining the Informed Consent of clinical trials' subjects will be followed.

A separate ICF will be available for the Focus Group Discussions (qualitative research part section 8.11).

